Rationale. The rationale for this aim is based on our preliminary data showing that RE-induced exosomes containing muscle-specific miR-1 enhance the catecholamine sensitivity of adipocyte. Further, microarray analysis identified a potential underlying mechanism for this enhanced catecholamine sensitivity that involves C/EBP α activation of β 3-AR expression via miR-1 down-regulation of AP-2 α , a repressor of C/EBP α . The purpose of this aim is to determine if this proposed mechanism is functionally operative by investigating 1) how RE-induced exosomes alter adipose metabolism both *in vivo* and *in vitro*, 2) the necessity of exosomal miR-1 in regulating adipose metabolism using miR-1 loss- and gain-of-function studies and 3) validating miR-1 predicted target gene AP-2 α . Given that our preliminary data were generated using male mice, for the proposed studies we plan to use both male and female mice to determine if sex has an influence on exosomal regulation of adipose catecholamine sensitivity.

Design. Based on preliminary data presented in Fig. 8A, we performed a power calculation to determine the number of mice required per group to detect significant ($p < 0.05$) difference between sham and synergist ablation groups. Male and female C57BL6/J mice (n=12/sex; 4 months of age) will undergo either sham (Control) or synergist ablation (RE) surgery which we have used extensively and previously described in detail^{24,66,84-86}. The synergist ablation model has been successfully used for over half a century as a resistance exercise mimetic in rodents to uncover the molecular and cellular mechanisms regulating skeletal muscle hypertrophy⁸⁷. One day post-surgery, skeletal muscle (plantaris), epididymal adipose and blood will be collected. Skeletal muscle and a portion (100 mg) of adipose tissue will be used to isolate total RNA to quantify miR-1 and gene expression by qPCR. Serum will be isolated from blood for exosome isolation as described in the SOP section.

Experiment 1.1. Control and RE exosomes will be incubated with 3T3-L1 adipocytes for 24 hr and then gene expression and catecholamine sensitivity measured as describe in the SOP.

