Experiment 1.2. To determine if miR-1 is necessary and sufficient to enhance adipocyte catecholamine sensitivity, Control exosomes will be transfected with miR-1 mimic (Control-plus) and RE exosomes with anti-miR-1 oligonucleotide (RE-minus). These modified exosomes will be incubated with 3T3-L1 adipocytes for 24 hr and then gene expression and catecholamine sensitivity measured as described in the SOP section.

Experiment 1.3. Based on our preliminary data, we hypothesize that RE-induced exosomal miR-1 is repressing expression of AP-2 α , a negative regulator of C/EBP α . To determine if AP-2 α is a target gene of miR-1 we will generate a luciferase reporter gene harboring the 3'-UTR of AP-2 α . We will assess the ability of miR-1 to

repress reporter gene expression; if so, then we will repeat the experiment with a mutant AP-2 α 3'-UTR reporter gene in which the predicted miR-1 binding site is mutated as previously described by us²⁴.

Experiment 1.4. Microarray analysis of epididymal adipose showed increased expression of genes involved in β -adrenergic signaling and lipolysis in response to RE that was blocked by GW4869 treatment (see Fig. 5). The purpose of this experiment is to use qPCR to confirm the microarray results and, importantly, determine if the observed changes in gene expression and effects of GW4869 treatment are the same in female mice (n=12/sex).

Statistical Analysis. A two-factor ANOVA (treatment X sex) will be used to determine if a significant interaction exists between factors for each dependent variable under consideration. If a significant interaction is detected, Scheffé post-hoc comparisons will be performed to identify the source of significance with $p \leq .05$.

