Experiment 2.1. The purpose of this experiment is to confirm our preliminary results showing the down-regulation of miR-1 in myotubes in response to electrical stimulation and if there is a corresponding increase in muscle-specific exosomal miR-1 abundance. If this relationship is confirmed, we will next treat myotubes with GW4869 to block exosome release to determine if the down-regulation of myotube miR-1 expression with electrical stimulation is mediated by the exosomal export of miR-1 as shown in vivo (see Fig. 4). The expression/abundance of miR-1 will be determined by qPCR as described in the SOP section.

Experiment 2.2. Exosomes from non-stimulated and stimulated myotubes will be incubated with primary human adipocytes for 24 hr and then gene expression and catecholamine sensitivity measured as described in the SOP section. Adult-derived human adipocyte stem cells (ADHASC) were isolated previously from lipo-aspirates⁹¹. [name] lab has expanded and frozen ADHASC from 6 different individuals available for these experiments. We will begin with one line which has been already shown to differentiate very reproducibly and determine the effect of exosomes derived from stimulated and non-stimulated myotubes on gene expression and catecholamine sensitivity as described in the SOP section.

Experiment 2.3. The purpose of this experiment will be to determine if muscle-specific exosomal miR-1 is necessary and sufficient to enhance adipocyte catecholamine sensitivity. Non-stimulated exosomes will be transfected with miR-1 mimic (Control-plus) while stimulated exosomes will be transfected with anti-miR-1 oligonucleotide (Stim-minus). These modified exosomes will then be incubated with primary human adipocytes for 24 hr and gene expression and catecholamine sensitivity measured as described in the SOP section.

Statistical Analysis. A two-factor ANOVA (treatment X sex) will be used to determine if a significant interaction exists between factors for each dependent variable under consideration. If a significant interaction is detected, Scheffé post-hoc comparisons will be performed to identify the source of significance with $p \leq .05$.

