Expected Outcomes & Alternative Approaches. We do not anticipate any technical issues with the planned experiments as we have experience with all of the described techniques. We also do not expect there to be any sex difference in the response of myotubes to electrical stimulation in terms of miR-1 expression in both myotubes and exosomes as Nielsen and colleagues reported no difference in miR-1 expression between men and women⁹². Further, we think that blocking exosome release with GW4869 treatment will prevent the down-regulation of miR-1 as well as the increase in exosomal miR-1 abundance. Finally there is the expectation that muscle-derived exosomal miR-1 will effectively enhance the catecholamine sensitivity and lipolysis of adipocytes through the up-regulation of β 3-AR signaling. Though somewhat minor, one concern we have is that myotube-derived exosomes will behave differently than exosomes isolated from serum; specifically, myotube-derived exosomes will not effectively deliver their cargo (i.e., miR-1) to adipocytes. To determine if this is the case, we will fluorescently label myotube-derived and serum-derived exosomes (see Fig. 2) to visualize their fusion kinetics with adipocytes. If we do find myotube-derived exosomes have limited fusion capability, we will switch to using primary myoblast cells derived from both male and female mice. We are confident these primary cell lines will produce functional exosomes as we have successfully used them to model how exosomes released from activated muscle stem cells are necessary for the proper remodeling of the extracellular matrix during muscle hypertrophy²⁴.

This aim also provides the opportunity to profile the miR content of muscle-specific exosomes. It is reasonable to expect that other muscle-specific miRs (myomiRs) are packaged into exosomes and delivered to other tissues. For example, muscle-specific miR-133a has been reported to regulate the expression of Prdm16 and brown adipogenesis⁹³.

Specific Aim 3: Determine if an acute bout of resistance exercise in humans promotes miR-1-mediated adipocyte lipolysis.

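### Aims 1 and 2 name no test of the treatment main effect; the only treatment comparisons in the stated rule follow a significant treatment-by-sex interaction

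*Combined protocol and SAP*

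**What the plan says.** The Statistical Analysis paragraphs of Specific Aim 1 and Specific Aim 2 use the same two sentences. The first says that a two-factor ANOVA, treatment by sex, "will be used to determine if a significant interaction exists between factors for each dependent variable under consideration". The second says: "If a significant interaction is detected, Scheffé post-hoc comparisons will be performed to identify the source of significance". The 0.05 level is attached to those comparisons. Neither paragraph names a test of the treatment main effect, or says what is tested or reported when the interaction is not significant.

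Other parts of the document bear on this:

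- Specific Aim 1, Design: "we performed a power calculation to determine the number of mice required per group to detect significant" differences between the sham and synergist ablation groups. That is a treatment contrast.
- Specific Aim 1, Rationale: "for the proposed studies we plan to use both male and female mice to determine if sex has an influence on exosomal regulation". Sex is an open question in Aim 1, and Experiment 1.4 returns to it for female mice.
- Specific Aim 2, Experiment 2.1: the stimulation effect on miR-1 is to be confirmed, and the GW4869 step depends on that confirmation.
- Specific Aim 2, Expected Outcomes: "We also do not expect there to be any sex difference in the response of myotubes to electrical stimulation in terms of miR-1 expression". The statement covers miR-1 in myotubes and exosomes only.
- Specific Aim 3, Statistical Analysis: the human analysis adjusts for sex and has no sex-interaction gate.

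**The concern.** Most experiments in Aims 1 and 2 ask whether exercise-induced or stimulation-induced exosomes change miR-1, gene expression or lipolysis. An effect that is real and equal in men and women, or in male and female mice, is a main effect with no interaction. The stated rule has no step that tests such an effect. It reaches a treatment comparison only when the sexes appear to differ.

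Two things are at stake. First, the test of the main hypothesis is left to be chosen after the data are seen, including for the go/no-go decision in Experiment 2.1. Second, if the rule is followed literally, the variables that do reach a treatment comparison are selected for an apparent sex difference. That favours chance sex-specific claims over a common effect.

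**Working it through.** **Inputs from the document.** Aim 1 has n=12/sex, which can be read as 12 per treatment-by-sex cell or as 12 per sex split over two groups (6 per cell). Aim 2 has 10 donor lines, 5 male and 5 female, giving 5 per cell.

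**Assumptions.** The interaction test is at 0.05, since its level is not stated separately. The text gives no effect size, SD or power for Aims 1 and 2, so the treatment effect δ (in SD units) is set at 1.0 and 1.5. For the same reason the Aim 1 sample size could not be reproduced. The layout is a 2×2 ANOVA with n independent observations per cell and error df = 4(n−1).

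**Step 1: no interaction.** The chance that the interaction test is significant equals its level, 0.05, whatever δ and n are. The route is therefore closed with probability 1 − 0.05 = 0.95 per variable. Simulation with 40,000 runs per scenario gave opening rates of 0.047 to 0.051.

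**Step 2: ungated main effect against the rule as written, no interaction.** The main-effect F test has noncentrality λ = nδ². The last column is the simulated chance that the interaction is significant and at least one within-sex Scheffé comparison is too.

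| n per cell | df | critical F | δ | λ | main-effect power | rule as written |
|---|---|---|---|---|---|---|
| 5 | 16 | 4.49 | 1.0 | 5 | 0.56 | 0.036 |
| 5 | 16 | 4.49 | 1.5 | 11.25 | 0.88 | 0.048 |
| 6 | 20 | 4.35 | 1.0 | 6 | 0.64 | 0.039 |
| 6 | 20 | 4.35 | 1.5 | 13.5 | 0.94 | 0.047 |
| 12 | 44 | 4.06 | 1.0 | 12 | 0.92 | 0.049 |
| 12 | 44 | 4.06 | 1.5 | 27 | >0.99 | 0.051 |

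**Step 3: a real interaction.** Let γ be the difference between the sexes in treatment effect, in SD units. The interaction test has λ = nγ²/4. The simulated chance that the route opens, with an average effect of 1.5 SD, is:

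| γ | n=5 | n=6 | n=12 |
|---|---|---|---|
| 0.5 | 0.08 | 0.09 | 0.14 |
| 1.0 | 0.18 | 0.22 | 0.40 |
| 1.5 | 0.35 | 0.42 | 0.72 |
| 2.0 | 0.56 | 0.64 | 0.92 |

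The 95% therefore does not carry over to variables with a substantial sex difference.

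**Step 4: shared donor lines in Aim 2.** Stimulated and unstimulated myotubes come from the same lines. If they are analysed as independent, the error term includes donor variation that cancels from the interaction contrast, and the test becomes too strict. With n=5, no interaction and assumed within-donor correlations of 0.3, 0.5 and 0.8, the simulated opening rate falls to 2.3%, 1.0% and 0.1%.

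**Step 5: several variables.** The chance that at least one of k independent variables opens by luck is 1 − 0.95^k. That is 1 − 0.95² = 0.10 for two variables and 1 − 0.95⁹ = 0.37 for nine, the number of genes listed in the gene expression SOP. Independence between genes is an assumption.

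**The case against.** A reader might infer that the main question of both aims goes untested 95% of the time. The document does not support that, for two reasons.

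- **The plan is silent on the main effect; it does not exclude it.** Only the Scheffé comparisons are conditional. A two-factor ANOVA yields a treatment main effect as standard output, and nothing forbids reporting it. The Aim 1 sizing and the confirmation step in Experiment 2.1 suggest the investigators mean to judge it. The supported statement is that the test is not specified.
- **The 95% is per variable and needs a true interaction of zero.** The plan expects that only for miR-1 in Aim 2. It does not say so for adipocyte gene expression or lipolysis, and in Aim 1 sex is a stated question, so testing the interaction there is legitimate.

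Three further limits stand. The effect sizes are assumptions. The independent 2×2 layout does not describe Experiments 1.2, 1.4 and 2.3, which involve more than two conditions once modified or inhibitor-treated arms are set beside their comparators, nor the paired lines of Aim 2. A reader might also fault the choice of Scheffé as too strict, but it is a valid procedure that covers complex contrasts, and replacing it would be a preference.

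It is also fair to say that these are mouse and cell-culture aims and that the human analysis in Aim 3 is unaffected. None of this supplies the missing test: the only treatment comparison written down still depends on the interaction.

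**Conclusion.** The point holds in limited form. Aims 1 and 2 specify no treatment main-effect test, and the treatment comparisons they do specify follow only a significant treatment-by-sex interaction. With no interaction that route is closed about 95% of the time per variable, given a 0.05 interaction test, and more often in Aim 2 if shared donor lines are treated as independent. The closed share does not depend on the size of the common effect, so a larger effect does not rescue it.

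The power contrast in Step 2 is an illustration that rests on the assumed 1.0 to 1.5 SD and on independent observations. It shows the direction and rough scale of what is lost if the rule is followed literally. It is not an estimate for any particular experiment in the plan. This is more than a missing detail, because the rule as written gives no treatment comparison for the very effect that Aim 1 is sized to detect.

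**What to change.** In the Statistical Analysis paragraphs of Specific Aims 1 and 2:

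1. Make the treatment effect, with sex in the model, the primary test. Always report it with a 95% CI, whatever the interaction shows. Where an experiment has more than two conditions (1.2, 1.4, 2.3), name the treatment contrasts in advance and test those.
2. Report the treatment-by-sex interaction, with its CI, as a separate test at a stated level. It remains a question of its own in Aim 1.
3. In Aim 2, include donor line as a repeated or random factor.

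Scheffé may stay for follow-up comparisons. The cost is analysis wording only; no extra animals, donor lines or assays are needed.

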Figure 10. Human exosomal miR-1 abundance following a bout of resistance exercise. Subjects performed a bout of resistance exercise (knee extension) to failure. Blood was collected pre- and post-exercise (0, 30, 60 and 90 minutes) followed by immediate isolation of exosomes from plasma and qPCR analysis of exosomal miR-1 abundance. Following resistance exercise, exosomal miR-1 abundance was trending higher after 30 and 60 minutes post-exercise, returning to baseline by 90 min. Data are presented as mean +/- SEM (n = 10).

used miR-1 as a readout of muscle-derived exosomes. To more rigorously test our working hypothesis that skeletal muscle-derived exosomes alter adipose metabolism, we have developed an *in vitro* model of RE using human myotubes. As shown in Fig. 9A-B, electrical stimulation of human myotubes appeared to increase myotube size compared to unstimulated myotubes and, importantly, resulted in a 5-fold increase in the abundance of miR-1 in exosomes isolated from the culture media (Fig. 9C). Moreover, there was a small decrease (9%) in myotube miR-1 expression with electrical stimulation (Fig. 9D). Although we were unable to run statistics because of insufficient “n” (n=2), the overall trend in myotube size and both exosomal and myotube miR-1 abundance follows the same general pattern shown in Fig. 1 for RE.

As an initial effort to test whether or not our working model translates into humans, we carried out a pilot study. Young, sedentary, adults (n=10, 5 females, 5 males) performed a bout of RE (knee extension) to failure. Blood was collected pre- and post-exercise (0, 30, 60 and 90 minutes). Exosomes were isolated from serum and miR-1 abundance quantified by qPCR. Thirty minutes

post-exercise there was a trend for an increase in exosomal miR-1 abundance. This result suggests that both mice and humans respond to RE in a similar manner by releasing miR-1 into the circulation through exosomes. Further, this pilot demonstrates we have the necessary expertise and infrastructure to successfully conduct the human RE study proposed in Aim 3.

Collectively, we have provided strong preliminary data to support a novel mechanism in which skeletal muscle, in response to RE, regulates adipose metabolism through the exosomal delivery of muscle-specific miR-1. Also, our preliminary data clearly demonstrate that we have both intellectual and technical expertise to successfully perform the proposed experiments.

APPROACH

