Rationale. Our preliminary data in mice suggest that RE enhances adipocyte catecholamine sensitivity through a novel mechanism involving the delivery of muscle-specific miR-1 to adipose via exosomes. The in vitro analyses in Aim 1 will explore this process mechanistically, with Aim 2 extending the analyses to primary human myotubes and adipocytes. The purpose of this aim is to determine if our working model translates to humans *in vivo*. Analyses of serum exosomes, muscle and adipose tissue isolated before and after a bout of RE will determine if miR-1 potentially mediates muscle-adipose crosstalk during exercise in humans. The ability of isolated exosomes to induce adipocyte lipolysis *in vitro* by enhancing catecholamine sensitivity through CEBP α activation of β AR-3 expression will be assessed.

Design. Relatively sedentary, generally healthy lean (BMI <25) and obese (BMI >30) men and women between 18-30 years of age without study contraindications will be recruited (see inclusion/exclusion criteria in Human Subjects section). Potential eligibility will be assessed by self-reported height and weight, and by reporting no participation in regular (>1 day per week) exercise for at least the past three months. All potential participants will arrive fasted to the Center for Clinical and Translational Sciences (CCTS). After giving written, informed consent, a detailed medical history form will be filled out to screen for eligibility. Measures of physical activity level will be collected before baseline blood, adipose, and muscle samples are taken. We intend to recruit an equal number of lean and obese participants (n=40 in each group, 20 men and 20 women). Power analysis based on the change we observed in miR-1 abundance in exosomes following a bout of knee extensions in a pilot study of 10 individuals, indicated that n=36 is required in each group. We are requesting n=40 in both the lean and obese groups based on an expected difference in means between 1 and 1.95 and an expected standard deviation of 0.45, with the power set at 0.8 and alpha at 0.05. This will accommodate 10% drop out prior to completing all biopsies.

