Adipose Biopsy. An abdominal subcutaneous fat biopsy sample will be obtained from the lower abdominal wall prior to and approximately 90 min post exercise. The adipose biopsy procedure is similar to the thigh muscle biopsy procedure, except that 1-2 g of adipose tissue is routinely obtained^{42,79,94,97,98}.

Human serum analyses. Glucose and insulin will be measured in the University of Kentucky CCTS Biochemical Analysis Laboratory^{99,100} from baseline serum collected from fasting lean and obese participants

to calculate HOMA-IR (Glucose*Insulin/405) as a measure of muscle insulin sensitivity. NEFA and free glycerol will be measured ⁸¹ both at baseline and in serum collected at multiple time points following the resistance exercise bout, and used to calculate a simplified “anti-lipolytic index” (NEFA*Insulin), which indicates adipocyte insulin sensitivity based on insulin’s ability to suppress lipolysis ¹⁰¹. In humans, fasting serum norepinephrine is positively associated with isoproterenol ED₅₀ in isolated adipocytes. Thus, elevated fasting catecholamines may be indicative of decreased adipose tissue catecholamine sensitivity ¹⁰². We will also measure serum epinephrine and norepinephrine by HPLC (Vanderbilt University Hormone & Analytical Services Core) ¹⁰³.

Statistical Analysis. The College of Health Sciences supports the effort of a biostatistician through the Office of Research to provide dedicated support to funded investigators. A one-way repeated measures ANCOVA adjusting by sex will be used to determine if a significant difference exists between the groups in response to RE for miR-1 and miR-1A/B primary transcripts. If a significant difference is detected, LSD *post-hoc* comparisons will be performed to identify the source of significance with $p \leq .05$. The Pearson correlation coefficient will be used to determine whether muscle, serum, and adipose miR-1 and miR-1A/B primary transcripts are correlated to tissue insulin sensitivity and fasting catecholamines at baseline. All statistical analyses will be performed using SAS[®] 9.4 (SAS institute, Cary NC).

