Expected outcomes and alternative approaches. We expect that the bout of lower extremity RE will result in decreased miR-1 abundance in muscle at 60 minutes, a rapid and transient increase in exosomal miR-1, and a subsequent increase in adipose miR-1 abundance at 90 minutes. We do not anticipate changes in miR-1 primary transcript abundance in adipose tissue which would support our hypothesis that miR-1 is delivered via exosomes. miR-1 is highly expressed in muscle and we acknowledge that a single bout of RE may not significantly decrease muscle miR-1 expression, even if it is packaged and released in exosomes. Moreover, 60 minutes post-exercise may not be the appropriate time point to detect this change. Our pilot time course blood sampling study following RE suggested that miR-1 in serum exosomes is highest at 30 minutes and is beginning to decrease by 1 hr post exercise. Thus, we expect delivery to adipose should be detectable at 90 minutes. We acknowledge that this time point may not enable us to capture any changes in downstream targets of miR-1, but will provide proof-of-principle for a large scale clinical exercise trial that would include additional post-exercise time points following an acute bout of RE, as well as a training component.

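### The Aim 3 power statement contradicts itself: means of 1 and 1.95 with SD 0.45 need 5 per group for 80% power, not the stated 36

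*Combined protocol and SAP*

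**What the plan says.** The sample-size basis for the human study is in Specific Aim 3, Design. It starts from a 10-person pilot of knee extension: "Power analysis based on the change we observed in miR-1 abundance in exosomes" is the stated source, and the analysis "indicated that n=36 is required in each group". The next sentence asks for 40 lean and 40 obese participants on the basis of an "expected difference in means between 1 and 1.95 and an expected standard deviation of 0.45", with power 0.8 and alpha 0.05. The margin over 36 is explained: "This will accommodate 10% drop out prior to completing all biopsies". The test, its sidedness, the scale of the measurement, and what the SD describes (one time point or the pre/post change) are not given. Nor is it said whether the powered comparison is pre versus post exercise or lean versus obese.

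The planned analysis (Specific Aim 3, Statistical Analysis) is a sex-adjusted repeated-measures ANCOVA "to determine if a significant difference exists between the groups in response to RE". The expected-outcomes text also anticipates a within-person effect, "a rapid and transient increase in exosomal miR-1". The Figure 10 caption in Preliminary Data reports the pilot as mean and SEM with n = 10. The only other power calculation is for Aim 1, where "we performed a power calculation to determine the number of mice required per group"; it does not bear on the human study.

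**The concern.** A difference of 0.95 against an SD of 0.45 is a standardised difference of 0.95/0.45 = 2.11. An effect that large needs only a handful of participants per group, so a requirement of 36 does not fit the inputs printed beside it.

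This is the only sample-size justification the document gives for a study in which 80 volunteers have muscle and adipose biopsies before and after exercise. If the SD is wrong, the stated precision is wrong. If the SD is right, 80% is not the power of the design. The difference matters most for the lean-obese comparison of response, because a null result there can be read only if one knows what difference the study could have detected.

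**Working it through.** **Inputs (Specific Aim 3, Design).** Means 1 and 1.95, so Δ = 0.95; SD σ = 0.45; power 0.80; α = 0.05, taken as two-sided because sidedness is not stated; stated result 36 per group; dropout 10%.

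**1. The plan's own figure.** The normal formula for two independent groups is n = 2(z₀.₉₇₅ + z₀.₈₀)²σ²/Δ² = 2 × (1.960 + 0.842)² × 0.45²/0.95² = 3.52, i.e. 4 per group. At so small an n the exact noncentral t is needed, with noncentrality Δ/(σ√(2/n)) and 2n − 2 degrees of freedom:

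| n per group | noncentrality | power |
|---|---|---|
| 4 | 0.95/(0.45 × √0.5) = 2.99 | 0.703 |
| 5 | 0.95/(0.45 × √0.4) = 3.34 | 0.831 |
| 36 | 0.95/(0.45 × √(2/36)) = 8.96 | above 0.999 |

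The answer is 5 per group, and 36/5 = 7.2. The stated 36 is not reproduced.

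**2. Other single readings, all with SD 0.45.**

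| Reading | n |
|---|---|
| Paired pre/post test, 0.45 as SD of the change | 5 in total (power 0.934; 4 gives 0.794) |
| Difference of 1.00 | 5 per group (0.867) |
| Difference of 1.95 | 3 per group (0.971) |
| Lean-obese difference in change, SD 0.45 at each time, correlation 0 assumed (SD of change 0.45√2 = 0.636) | 9 per group (0.844) |
| Bonferroni for 20 tests (assumed) | 10 per group (0.862) |
| Group-by-sex interaction of 0.95 (assumed) | 16 per group (0.822) |

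**3. Is 36 a misprint?** No. 36/0.90 = 40, and Table 1 recruits 27 + 27 + 26 = 80 = 2 × 40. The sample size is consistent throughout, so the fault lies in the inputs or their labels.

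**4. The SD that 36 implies.** Solving for σ at n = 36, Δ = 0.95 and 80% power gives 1.42 (two-sample exact t), 1.44 (two-sample normal formula) or 1.98 (paired exact t).

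**5. A possible cause.** If 0.45 were the SEM of the 10-person pilot, the SD would be 0.45 × √10 = 1.423. The normal formula then gives 2 × (2.802)² × 1.423²/0.95² = 35.2, i.e. 36 per group; exact t gives 37. The match is suggestive, but no readable text ties 0.45 to that SEM.

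**6. What 36 per group can do under each SD of the response.** These are plain two-sided t tests, for illustration only; they are not the planned ANCOVA.

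| | SD 0.45 | SD 1.42 (assumption) |
|---|---|---|
| Within-group change of 0.95, power | above 0.999 | 0.973 |
| Detectable within-group change | 0.22 | 0.68 |
| Lean-obese difference of 0.95, power | above 0.999 | 0.798 (0.839 at 40) |
| Lean-obese difference of 0.475, power | 0.993 | 0.287 |
| Detectable lean-obese difference | 0.30 | 0.95 |

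If 1.42 were the SD at each time point and not of the change, a pre/post correlation between 0 and 0.75 (assumed range) would move the power for 0.95 at 36 per group from 0.79 to above 0.999 within a group, and from 0.51 to 0.98 between groups. That is why the sentence must say what its SD describes.

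**The case against.** Four points deserve weight.

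- **Stacked assumptions can reach 36.** A group-by-sex interaction of 0.95 in the pre/post change (SD of change 0.636) needs 30 per group, or 36 with a Bonferroni correction for two tests. A lean-obese difference in change of 0.475 with the same SD gives the same two figures. But the plan states none of these assumptions, so they do not reconcile the sentence. The defensible claim is that the inputs as written, under a simple two-sample or paired test or any single variant listed above, do not give 36.
- **The sample size itself may be sound.** If only the SD label is wrong, 36 stands, or nearly so. The contradiction must not be read as saying the study is seven times too large. This stands in full. The pilot rise being described only as a trend also fits an SD larger than 0.45.
- **The practical harm is limited.** The within-group rise is well powered if the SD of the change is either 0.45 or 1.42, and a lean-obese difference of 0.95 has about 80% power even at 1.42. Aim 3 is described as proof-of-principle. This narrows the harm to the lean-obese question. It does not remove it, because for half that difference the power is 99% or 29% depending on the SD.
- **Detail may sit elsewhere.** The Design text refers to a Human Subjects section that is not in the supplied text. A fuller calculation there could explain the source of the 36, but it would not make the printed inputs agree with the printed result.

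**Conclusion.** The concern holds. As printed, the inputs require 5 per group and the stated requirement is 36, about a 7-fold disagreement; 80% is not the power of 36 per group under those inputs. This rests on arithmetic alone, with a two-sided test assumed. A one-sided test would need still fewer (4 per group).

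The SEM explanation is a possibility of low to moderate confidence, and the conclusion does not depend on it. What remains unknown is the detectable lean-obese difference in response at 36 per group: about 0.30 or about 0.95 according to which SD is true. The sole stated sample-size basis for the human study should be corrected before it is relied on. Nothing here supports reducing enrolment.

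**What to change.** Re-run the calculation from the existing pilot data and replace the power sentence in Specific Aim 3, Design. The new text should give:

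- the verified SD, and whether it is the SD at one time point or of the pre/post change;
- the measurement scale, the test and the sidedness;
- whether the powered comparison is the pre/post change or the lean-obese difference in response that the Statistical Analysis section tests;
- at 36 per group, the power and the detectable lean-obese difference (about 0.30 if the SD of the response is 0.45, about 0.95 if it is 1.42).

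If the pilot data confirm it, state that 0.95 is the pilot pre/post change and not an expected lean-obese difference. The cost is one corrected statement and one re-run from data already in hand, with no change to enrolment.
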